1.1 Study Design

Overall Design

This will be a single centre, eight week, randomized, examiner-blind, three treatment, parallel group design, stratified study in healthy subjects, with at least two sensitive teeth that meet all of the study criteria at the Screening and Baseline visits. DH will be assessed at Baseline, and after 4 and 8 weeks of twice daily treatment.

At the Screening visit, subjects will give their written informed consent to participate in the study. Demography, medical history and concomitant medications will be recorded, followed by an oral examination. This will include an oral soft tissue (OST) examination, an oral hard tissue examination (OHT), dentition exclusions, assessment of erosion, abrasion, recession (EAR), gingival status, tooth mobility and subject response to a qualifying air sensitivity assessment, subject response will be recorded as a numerical value (Schiff score 2/3). Eligible subjects will be supplied with a standard fluoride dentifrice and a fluoride oral rinse to use twice daily (morning and evening) during the acclimatization period between the Screening and Baseline visits. Each product use will be recorded in the diary provided. First use of the acclimatization dentifrice and oral rinse will be carried out under supervision at the study site.

At the Baseline visit (2-3 weeks after Screening), eligibility to continue will be assessed. Subjects will undergo an OST examination, followed by tooth sensitivity assessments (a tactile stimulus [Yeaple probe, maximum 20g pressure], then an evaporative air stimulus [with Schiff Sensitivity Scale and Visual Rating Score VRS]), and a review of the inclusion/exclusion criteria. Two test teeth will then be identified and eligible subjects will be randomized to treatment (stratified by maximum baseline Schiff sensitivity score of the two selected test teeth). First use of allocated study product will be carried out under supervision at the study site, after the supervised brushing subjects will be requested to measure out the dose of the oral rinse using the dosing cup provided. Subjects will continue to use their assigned study treatment twice daily (morning and evening) for the next 8 weeks, recording each brushing and rinsing occasion in the diary provided.

Subjects will return to the study site each week (Visits 3, 4, 5, 6, 7, 8, 9 and 10) over the eight week study period and asked to return their study kit so that the oral rinse bottle and its contents can be weighed to verify study compliance. Diaries will also be checked at each visit. A supervised brushing and rinse will also be conducted at each visit (except Visit 10). Following supervised product use all products will be returned to the subject. The dentifrice and oral rinse will be re-dispensed at Visit 6 (Week 4). Tooth sensitivity will be re-assessed after 4 and 8 weeks (Visits 6 and 10) of treatment, using first a tactile stimulus (Yeaple probe, maximum 80g pressure) and then an evaporative air stimulus (with Schiff Sensitivity Scale and VRS) on the two selected test teeth only. An OST examination will be completed at each of these visits, prior to the clinical assessments of sensitivity.

The study site will send twice daily (morning and evening) short message service (SMS) reminders requesting that subjects remember to conduct their timed brush and rinse in the morning and evening.

For further details please refer to Section 3.1 of the protocol.

1.2 Study Objectives

Objectives	Endpoints
Primary Objective	Primary Endpoint

 To evaluate and compare the clinical efficacy of a 1.5% KOX containing oral rinse for the relief of DH, as elicited by an evaporative air stimulus (with Schiff Sensitivity Scale), against a negative control oral rinse, following use as an adjunct to twice daily brushing with a standard fluoride dentifrice, after 8 weeks. 	
 Change from baseline in Schiff sensitivity score at 8 weeks.
Secondary Objectives	Secondary Endpoints
To evaluate and compare the clinical efficacy of a 1.5% KOX containing oral rinse for the relief of DH, as elicited by a tactile stimulus (Yeaple probe), against a negative control oral rinse, following use as an adjunct to twice daily brushing with a standard fluoride dentifrice, after 8 weeks.	
 Change from baseline in tactile threshold (Yeaple probe) at 8 weeks.
Exploratory Objectives	Exploratory Endpoints

Objectives	Endpoints

 To evaluate and compare the clinical efficacy of a 1.5% KOX containing oral rinse for the relief of DH, as elicited by an evaporative air stimulus (with Schiff Sensitivity Scale), against a placebo oral rinse, following use as an adjunct to twice daily brushing with a standard fluoride dentifrice, after 8 weeks. 	
 Change from baseline in Schiff sensitivity score at 8 weeks.

 To evaluate and compare the clinical efficacy of a 1.5% KOX containing oral rinse for the relief of DH, as elicited by a tactile stimulus (Yeaple probe), against a placebo oral rinse, following use as an adjunct to twice daily brushing with a standard fluoride dentifrice, after 8 weeks. 	
 Change from baseline in tactile threshold (Yeaple probe) at 8 weeks.

 To evaluate and compare the clinical efficacy of a 1.5% KOX containing oral rinse for the relief of DH, as elicited by an evaporative air stimulus (with Schiff Sensitivity Scale), against a marketed negative control oral rinse and a placebo oral rinse, following use as an adjunct to twice daily brushing with a standard fluoride dentifrice, after 4 weeks. 	
 Change from baseline in Schiff sensitivity score at 4 weeks.

 To evaluate and compare the clinical efficacy of a 1.5% KOX containing oral rinse for the relief of DH, as elicited by a tactile stimulus (Yeaple probe), against a marketed negative control oral rinse and a placebo oral rinse, following use as an adjunct to twice daily brushing with a standard fluoride dentifrice, after 4 weeks. 	
 Change from baseline in tactile threshold (Yeaple probe) at 4 weeks.

 To evaluate and compare the clinical efficacy of a 1.5% KOX containing oral rinse for the relief of DH, as elicited an evaporative air stimulus (with VRS), against a marketed negative control oral rinse and a 	
 Change from baseline in Visual Rating Score (VRS) at 4 and 8 weeks.

Objectives	Endpoints

placebo oral rinse, following use as an adjunct to twice daily brushing with a standard fluoride dentifrice, after 4 and 8 weeks.
	

 To evaluate and compare the clinical efficacy of a 1.5% KOX containing oral rinse for the relief of DH, as elicited by an evaporative air stimulus (with Schiff Sensitivity Scale), against the efficacy of the group obtained by combining the marketed negative control and the placebo oral rinse, following use as an adjunct to twice daily brushing with a standard fluoride dentifrice, after 4 and 8 weeks. 	
 Change from baseline in Schiff sensitivity score at 4 and 8 weeks.

 To evaluate and compare the clinical efficacy of a 1.5% KOX containing oral rinse for the relief of DH, as elicited by a tactile stimulus (Yeaple probe), against the efficacy of the group obtained by combining the marketed negative control and the placebo oral rinse, following use as an adjunct to twice daily brushing with a standard fluoride dentifrice, after 4 and 8 weeks. 	
 Change from baseline in tactile threshold (Yeaple probe) at 4 and 8 weeks.

 To evaluate and compare the clinical efficacy of a 1.5% KOX containing oral rinse for the relief of DH, as elicited an evaporative air stimulus (with VRS), against the efficacy of the group obtained by combining the marketed negative control and the placebo oral rinse, following use as an adjunct to twice daily brushing with a standard fluoride dentifrice, after 4 and 8 weeks. 	
 Change from baseline in VRS at 4 and 8 weeks.

1.3 Treatment

	Test Product	Negative control	Placebo Product
Product Name	Experimental oralrinse containing 1.5% KOX, 0ppm fluoride, pH 7	Oral rinse containing 0.02% w/w NaF. Colgate Total Daily Repair® (USA marketed product)	Oral rinse containing 0% KOX and 0 ppmfluoride, pH
Product Formulation Code (MFC)	CCI	Commercially Available	CCI
Route of Administration	Oral	Oral	Oral
Dosing Instructions	Rinse twice daily (morning and evening) with 10 ml of oral rinse for 60 timed seconds and expectorate. No further rinsing with water will be permitted after use of the oral rinse.	Rinse twice daily (morning and evening) with 10 ml of oral rinse for 60 timed seconds and expectorate. No further rinsing with water will be permitted after use of the oral rinse.	Rinse twice daily (morning and evening) with 10 ml of oral rinse for 60 timed seconds and expectorate. No further rinsing with water will be permitted after use of the oral rinse.

All subjects will receive the same regular fluoride dentifrice and a US marketed oral rinse during the acclimatization period to familiarise themselves with the required brushing and rinsing regimen, and standardise oral hygiene practices.

Subjects will apply a full brush head of the standard fluoride dentifrice, brush for one timed minute (in their usual manner) and expectorate; rinse with 10 ml of tap water for 5 seconds and expectorate; and then rinse with 10 ml of their randomly assigned oral rinse for 60 timed seconds and expectorate. No further rinsing with water will be permitted after use of the oral rinse, and subjects will be asked to refrain from eating or drinking within 30 minutes of using the oral rinse. The dosage regimen of twice daily treatment (morning and evening) will be the same for all subjects.

1.4 Sample Size Calculation

A sufficient number of healthy subjects will be screened to randomise at least 100 subjects (approximately 50 to the experimental treatment, 25 to the negative control and 25 to placebo) to ensure 80 evaluable subjects complete the entire study. This will ensure approximately 40 evaluable subjects for the test treatment and 20 each for the negative control treatment and placebo.

With this 2:1:1 distribution of the subjects in the treatment arms, the study has less than 50% power to detect a mean treatment difference of 0.36 in the Schiff sensitivity score using a two-sided t-test of significance level 0.05 for the experimental product against the negative control. The standard deviation used in this calculation is 0.8; this estimate is obtained from the GSKCH study 204763. When the experimental treatment group is compared with the combined group comprising of the negative control group and the placebo group using the two-sided t-test with the same estimates of mean difference, significance level and standard deviation, the study will have 51.1% power.

The magnitude of the treatment difference is more important and is expected to be in favour of the experimental mouthwash.

2 Planned Analyses

2.1 Interim Analysis

No interim analysis is planned.

2.2 Final Analyses

The final planned primary analyses will be performed after the completion of the following sequential steps:

1. All subjects have completed the study as defined in the protocol.
2. All required database cleaning activities have been completed and database has been locked.
3. All criteria for unblinding the Randomization codes have been met and the Randomization codes have been distributed.

3 Considerations for Data Analyses and Data Handling Conventions

3.1 Baseline Definition

For all endpoints the baseline value will be the latest Day-0 pre-dose assessment with a non-missing value.

Unless otherwise stated, if baseline data is missing no derivation will be performed and will be set to missing.

3.2 Subgroups/Stratifications

Eligible subjects will be stratified according to their maximum baseline Schiff sensitivity score of the two selected teeth. The stratification factor will give rise to two strata.

Stratum 1: Subjects with maximum baseline Schiff sensitivity score of 2 for the two selected test teeth.

Stratum 2: Subjects with the maximum baseline Schiff sensitivity score of 3 for the two selected test teeth.

Efficacy variables will be analyzed accounting for strata.

Subgroups are not defined for this trial.

3.3 Centers Pools

This is a single centre study, therefore pooling of centers is not required.

3.4 Timepoints and Visit Windows

The study schedule should be followed as per protocol. Deviations from the study schedule with respect to visit timings will be reviewed on a case-by-case basis to determine whether the data should be excluded from the Per-Protocol (PP) analysis (Section 4.1.2).

4 Data Analysis

Data analysis will be performed by inVentiv Health Clinical. The statistical analysis software used will be SAS version 9.4 (Studio).

Prior to database closure a Blinded Data Review Meeting (BDRM) will be conducted in which various aspects of the trial will be discussed and agreed.

Unless otherwise described below, all listings will be produced for all randomized subjects.

4.1 Populations for Analysis

4.1.1 Subject Disposition

Screen failures will be defined as subjects who do not satisfy all of the inclusion/exclusion criteria. A summary will be provided of the number of subjects screened and the number of screen failures with reasons why subjects were not randomized (Table 14.1.1). Percentages will be based on the total number of subjects randomized.

Subject disposition will also be summarized as the number and percentage of subjects who complete the study, with the number who discontinue broken down by reason for discontinuation (Table 14.1.1). The percentages are based on the total number of subjects randomized. The table will also summarise the number and percent of subjects assigned to each analysis population (defined in Section 4.1.3). The summary will be presented by treatment and overall.

Subject disposition including the subject status (completer, Yes/No), critical demographic data (age, sex, race and ethnicity), the duration of treatment before discontinuation and the specific reason for discontinuation, will be listed by treatment group for randomized subjects ([Listing 16.2.1.1](#)) and non-randomized subjects ([Listing 16.2.1.2](#)) separately.

4.1.2 Protocol Deviations

Important major protocol deviations (including deviations related to study inclusion/exclusion criteria, conduct of the trial, patient management or patient assessment) will be summarized and listed.

Protocol deviations will be tracked by the study team throughout the conduct of the study. Data will be reviewed prior to unblinding and closure of the database to ensure all important deviations are captured and categorized.

Major deviations of the protocol procedures identified as liable to influence the efficacy outcome may include, but will not be necessarily limited to, the following:

- Violations of inclusion or exclusion criteria
- Prior / concomitant medications
- Ineligible teeth
- Treatment non-compliance
- Not receiving randomized treatment
- Visit outside the planned schedule

Further deviations liable to influence the efficacy outcome will be given in the Review Listing Requirement (RLR) document where major deviations will be identified at the blinded data review meeting. The number and percentage of subjects with any major protocol deviations and with each type of major protocol deviations will be presented by treatment ([Table 14.1.2](#)) and listed in [Listing 16.2.2.1](#). Any minor protocol deviations will be listed similarly ([Listing 16.2.2.2](#)).

4.1.3 Analysis Populations

Five analysis populations are defined.

Population	Definition / Criteria	Analyses Evaluated
All Screened Subjects	
 • All subjects who enter the study and sign the informed consent form. This population includes screen failures as well as those that are randomized 	
 • Disposition, AE listing

Population	Definition / Criteria	Analyses Evaluated
Randomized	
 All subjects who are randomized and may or may not receive the application of the study products. Any subject who receives a treatment Randomization number will be considered to have been randomized 	
 Protocol violations
Safety	
 Comprise of all randomized subjects who receive at least one dose of study treatment. This population will be based on the treatment the subject actually received. 	
 Safety
Intent-To-Treat	
 Comprise of all randomized subjects who receive at least one dose of study treatment and have at least one post-baseline efficacy evaluation. This population will be based on the treatment to which the subject was randomized. 	
 Efficacy
Per-Protocol	
 The 'Per-Protocol' (PP) population will include all subjects in the ITT population who have no protocol deviations deemed to affect efficacy. 	
 Efficacy

The primary population for assessment of efficacy will be the ITT population. A PP analysis will be performed on the primary and secondary efficacy variable if more than 10% of the subjects in the ITT population are excluded from the PP population.

The numbers of subjects included in each of the populations, and the number excluded from each population broken down by the reason for exclusion will be presented ([Table 14.1.2](#)). Subjects excluded from any of the analysis populations will be listed ([Listing 16.2.3.1](#)).

4.2 Subject Demographics and Other Baseline Characteristics

4.2.1 Demographic Characteristics

Descriptive statistics (number of subjects, mean, standard deviation, median, minimum and maximum for continuous variables, and frequency and percentage for categorical variables) will be presented for demographic data by treatment group and overall. These data include age, gender, race, ethnicity and Schiff stratification categories and will be presented for the Safety ([Table 14.1.4.1](#)), ITT ([Table 14.1.4.2](#)) and if required the PP populations ([Table 14.1.4.3](#)).

Demographic information will be listed ([Listing 16.2.4.1](#)) for all randomized subjects.

4.2.2 General Medical History

Medical history data will be listed ([Listing 16.2.4.2](#)) with start date and end date or ongoing at the start of study drug. A data listing will also be produced for evaluation of protocol violations at the blinded data review stage.

4.3 Study Product Compliance and Use of Other Therapy

Supervised brushing/rinsing non compliance (subject number, date of visit and time of the supervised procedure and reason why the supervised brushing was not performed according to the protocol) will be listed for the blinded data review and specified in the RLR document.

4.3.1 Study Product Compliance and Exposure

Brushing/rinsing compliance (using study product twice daily) will be listed for the blinded data review and specified in the RLR document.

4.3.2 Prior and Concomitant Medication

Prior medications will be listed by subject, with, indication, dose, dose form, frequency, route, start date and end date ([Listing 16.2.5.1](#)). Prior medications are defined as those stopped before the first administration of the study products. Concomitant medications will be listed similarly ([Listing 16.2.5.2](#)). Concomitant medications are defined as those ongoing or started on or after the first administration of the study products.

4.3.3 Other Therapy/Rescue Medication

Not Applicable.

4.4 Analysis of Efficacy

4.4.1 Primary Efficacy Endpoint

4.4.1.1 Primary Efficacy Endpoint Definition

The change from baseline in Schiff sensitivity score at Week 8 is the primary efficacy endpoint.

The subjects Schiff sensitivity score will be derived as the mean of the two test teeth at each visit assessed and the change from baseline will be derived from this mean Schiff score. For for post-baseline observations, the average will be calculated only across teeth that have both a valid baseline and a valid postbaseline assessment.

Summary statistics of the observed mean Schiff sensitivity scores and changes from baseline will be presented by treatment at Baseline, Week 4 and Week 8 ([Table 14.2.1.1.1](#)).

To visually inspect the treatment effect on Schiff sensitivity scores, a plot across time, with the raw means together with standard error (SEs) bars will be produced. The plot will display a different symbol line for each treatment group ([Figure 14.2.1](#)).

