9.2.6. Handling of Dropouts and Missing Data

Dropouts and missing data are expected to be low (only 2.3% subjects were discontinued or had missing data after randomisation in the 8 week GSKCH study 204763). A robustness analysis based on worst case imputation might be elaborated in the SAP.

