4.4.1.2 Statistical Hypothesis, Model, and Method of Analysis

The primary analysis is a comparison of the mean change from baseline Schiff sensitivity score between Test Product and Negative Control at Week 8.

The null hypothesis for the primary endpoint is that the mean change from baseline in Schiff sensitivity score is equal between the two products.

$$H_0: \mu_1 = \mu_2$$

The alternative hypothesis is that the mean change from baseline in Schiff sensitivity score is not equal between the two products.

$$H_1: \mu_1 \neq \mu_2$$

The change from baseline in Schiff sensitivity score at Week 8 will be analyzed using ANCOVA with treatment as factor and mean baseline Schiff sensitivity score as covariate. Note that since the baseline Schiff sensitivity score will be included as a covariate, the baseline Schiff stratification value will not be included in the model. Adjusted means of all treatments and their SEs, P-value and 95% confidence interval (CIs) will be presented on the ITT population (Table 14.2.1.1.2). Treatment differences of the treatment comparisons will also be provided together with P-values and 95% CIs.

The assumption of normality and homogeneity of variance in the ANCOVA model will be investigated and if violated, data transformations will be investigated. If suitable transformations cannot be found, non-parametric Van Elteren tests will be performed adjusting for the maximum baseline Schiff sensitivity scores and results will be compared with the ANCOVA results. If the inferences from the two analyses are similar then both sets of results will be reported and emphasis will be made on the ANCOVA results. In case of discrepancies between p-values of ANCOVA and Van Elteren analysis, inferences will be drawn on the non-parametric analysis.

To visually inspect the treatment effect on Schiff sensitivity scores, a plot across time (Baseline, Week 4 and Week 8) will be displayed with raw means and SE bars. The plot will display a different symbol line for each treatment group (Figure 14.2.1).

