4.5 Analysis of Secondary Objectives

4.5.1 Efficacy (Secondary)

The change from baseline in tactile threshold at Week 8

The change from baseline in tactile threshold at Week 8 is the secondary efficacy endpoint.

The null hypothesis for the secondary endpoint is that the mean change from baseline in tactile threshold is equal between the two products.

$$H_0: \mu_1 = \mu_2$$

The alternative hypothesis is that the mean change from baseline in tactile threshold score is not equal between the two products.

$$H_1: \mu_1 \neq \mu_2$$

The primary treatment comparison of this secondary efficacy variable is:

Test Product versus Negative Product at Week 8.

All other treatment comparisons based on secondary efficacy variable are part of the exploratory objectives.

The subjects tactile threshold will be derived as the mean of the two test teeth at each visit assessed and the change from baseline will be derived from this mean tactile threshold. If tactile threshold for test teeth reported greater than 80g for post baseline assessment then in that case it will be consider as 90g.

Summary statistics of the observed mean tactile threshold scores and changes from baseline will be presented by treatment at Baseline, Week 4 and Week 8 (Table 14.2.2.1).

The change from baseline in tactile threshold at Week 8 will be calculated as the subject level mean change from baseline (on the two test teeth) and analyzed at Week 8 using ANCOVA with treatment and baseline Schiff stratification value as factors and baseline tactile threshold included as a covariate. Adjusted means of all treatments and their SEs, P-value and 95% CIs

will be presented. Treatment differences of all pairs of treatments will be provided together with P-values and 95% CIs (Table 14.2.2.2).

To visually inspect the treatment effect on tactile threshold scores, a plot across time, with the raw means together with SE bars will be produced. The plot will display a different symbol line for each treatment group (Figure 14.2.2).

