4.6 Analysis of Exploratory Objective

Exploratory analysis based on the primary and secondary efficacy variable (change from baseline in Schiff sensitivity score and change from baseline in tactile threshold) are discussed in the section above.

Raw values of the visual rating score (VRS) (averaged over the two test teeth) at Week 4 and Week 8 together with changes from baseline will be summarized by treatment at each study time point (Table 14.2.3.1). To visually inspect the treatment effect on Schiff sensitivity

scores, a plot across time, with the raw means together with SEs bars will be produced. The plot will display a different symbol line for each treatment group (Figure 14.2.3).

The change from baseline in VRS will be calculated as the subject level mean change from baseline (on the two test teeth) and analyzed separately at Week 4 and 8 using ANCOVA with treatment and baseline Schiff stratification value as factors and baseline VRS score included as a covariate. Adjusted means of all treatments and their SE, P-value and 95% CIs will be presented. Treatment differences of all pairs of treatments will be provided together with P-values and 95% CIs (Table 14.2.3.2).

The assumption of normality and homogeneity of variance in the ANCOVA model will be investigated and if violated, data transformations will be investigated. If suitable transformations cannot be found, non-parametric Van Elteren tests will be performed adjusting for the maximum baseline Schiff sensitivity scores and results will be compared with the ANCOVA results. If the inferences from the two analyses are similar then both sets of results will be reported and emphasis will be made on the ANCOVA results. In case of discrepancies between p-values of ANCOVA and van Elteren analysis, inferences will be drawn on the non-parametric analysis.

Analyses for the Combined Control group will also be performed on the change from baseline in VRS to Weeks 4 and 8 using the same ANCOVA model mentioned above .

The adjusted mean for each treatment, and the difference between the pairs of treatments together with their corresponding 95% CIs and the p-values for treatment comparisons, will be provided (Table 14.2.3.2).

Test Product versus Combined Control group will be obtained by using contrast at Week 4 and 8.

All data for each efficacy measure will be presented for each subject at Baseline, Week 4 and Week 8 (Listing 16.2.6.1, Listing 16.2.6.2 and Listing 16.2.6.3).

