[1] Age in years; Sex: F = Female, M = Male; Race: A = Asian, B = Black or African American, I = American Indian or Alaska Native, H = Native Hawaiian or Other Pacific Islander, W = White, M = Multiple; Ethnicity: H = Hispanic or Latino, NH = Not Hispanic or Latino.

Page x of y

PPD

Programming Note : 1) Subject level average is based raw values for selected 2 test teeth.

2) Please create a similar listing for tactile and VRS score

1.5% w/w dipotassium oxalate monohydrate (KOX) and 0 ppm fluoride oral rinse
207656

Final Statistical Reporting and Analysis plan V1.0 5 Oct 2017

Protocol 207656

Program Run Date:xxxx

Listing 16.2.7.1
All Adverse Events
Randomized Population

Study Population: Randomized (N=xx)
Treatment Group: Test Product 1

Subject Number	Age/Sex/ Race/ Ethnicity [1]	Adverse Event (Preferred Term) (System Organ Class)	Start Date /Study Day[2]	Start Time	End Date	End Time	Frequency /Intensity [3]	Related to Study Product?	Action Taken re Study Product	Outcome	Serious?	Withdrew? [4]
PPD		HEADACHE (NERVOUS SYSTEM DISORDER) [Non-Oral]	PPD			20:30	MILD	No	NOT APPLICABLE	RECOVERED/ RESOLVED	NO	NO

@@ Adverse events with verbatim text ending in this are classified as Oral AEs.

[1] Age in years; Sex: F = Female, M = Male; Race: A = Asian, B = Black or African American, I = American Indian or Alaska Native, H = Native Hawaiian or Other Pacific Islander, W = White, M = Multiple; Ethnicity: H = Hispanic or Latino, NH = Not Hispanic or Latino.

[2] Study day is the day relative to start of treatment, day 1 being the day of first treatment.

[3] INT = Intermittent and SGLE = Single.

[4] Did subject withdraw from study as a result of this adverse event?

Page x of y

PPD

Programming Note for Listing 16.2.7.2:

- Repeat the same layout for listing 16.2.7.2
- Population should be used 'Non randomized Subjects'
- The fourth column should be only 'Start Date'

GlaxoSmithKline Consumer Healthcare Confidential

[figure not shown]
1.5% w/w dipotassium oxalate monohydrate (KOX) and 0 ppm fluoride oral rinse
207656

Final Statistical Reporting and Analysis plan V1.0 5 Oct 2017

- *Add footnote 'Only SAEs are collected for non randomized subjects'*
- *Delete the footnote related to study day and adjust the numbers accordingly.*

Figure 14.2.1
Evaporative (Air) Sensitivity Schiff Sensitivity Score by Time and Treatment
Intent to Treat Population

Study Population: Intent-to-Treat (N=XX)

*Mean and SE plotted are from summary statistics in T 14.2.1.1.1

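### Does the one-tooth rule in SAP 4.4.1.1 give a wrong change from baseline because the baseline mean is not limited to the same tooth?

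*SAP*

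**What the plan says.** SAP 4.4.1.1 defines the subject's score: "The subjects Schiff sensitivity score will be derived as the mean of the two test teeth at each visit assessed". Change is derived from that mean. A further sentence, confined to post-baseline observations, says that "the average will be calculated only across teeth that have both a valid baseline and a valid postbaseline assessment".

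Nothing else in the SAP says which teeth enter the baseline mean when one tooth drops out:

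- Section 3.1 fixes which assessment counts as baseline: "For all endpoints the baseline value will be the latest Day-0 pre-dose assessment with a non-missing value".
- Section 4.4.1.2 specifies "ANCOVA with treatment as factor and mean baseline Schiff sensitivity score as covariate".
- The programming note to Listing 16.2.6.1 says "Subject level average is based raw values for selected 2 test teeth".
- For tactile threshold, section 4.5.1 first says "The subjects tactile threshold will be derived as the mean of the two test teeth at each visit assessed" and later speaks of a subject-level mean change. Section 4.6 uses the mean-change wording for VRS. Neither section has a one-tooth rule.

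SAP 4.4.3 rules out imputation.

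**The concern.** The restriction matters only when one of the two teeth lacks a valid score, and in that case it seems to cover half the calculation. The post-baseline mean shrinks to one tooth while the baseline mean stays at two. If the teeth started at different levels, the subtraction mixes a real change with a change in which teeth are averaged. A subject with baseline scores 2 and 3 whose more sensitive tooth is not evaluable would look half a point better than the remaining tooth shows.

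This is the primary endpoint, and two programmers could produce different values from the same data. The value also enters the summary table, the listing and, if change is what is ranked, the van Elteren fallback. Under SAP 4.4.1.2 that fallback decides the inference if it disagrees with the ANCOVA.

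**Working it through.** **Inputs.** Test teeth need a baseline Schiff score of at least 2 (Protocol 4.1, criterion 4d) on a 0 to 3 scale (Protocol 6.2.3.1), so the possible pairs are 2/2, 2/3 and 3/3. SAP 1.4 gives a difference of 0.36, SD 0.8, two-sided 0.05 and about 40/20/20 evaluable subjects.

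**The plan's own figure.** Two-sample t-test, 40 v 40: SE = 0.8 × √(1/40 + 1/40) = 0.179, noncentrality 0.36/0.179 = 2.01, power 51.1%, as stated. For 40 v 20: SE = 0.8 × √(1/40 + 1/20) = 0.219, power 36.6%, which agrees with the stated less than 50%.

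**Subject level.** Let the remaining tooth score 1 after baseline.

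| Baseline pair | Tooth missing | Literal change | Matched change | Literal − matched |
|---|---|---|---|---|
| 2/2 | either | 1 − 2 = −1.0 | 1 − 2 = −1.0 | 0 |
| 2/3 | the 3 | 1 − 2.5 = −1.5 | 1 − 2 = −1.0 | −0.5 |
| 2/3 | the 2 | 1 − 2.5 = −1.5 | 1 − 3 = −2.0 | +0.5 |
| 3/3 | either | 1 − 3 = −2.0 | 1 − 3 = −2.0 | 0 |

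The post-baseline score cancels, so the gap is the same whatever the remaining tooth scores.

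**Which value is nearer the endpoint?** The endpoint is the change in the two-tooth mean, and with one tooth missing that quantity is unobserved. Suppose that, within a mouth, a tooth's Week 8 score rises by s for each baseline point. For a 2/3 pair the expected error is:

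- literal: half the expected gap between the teeth = 0.5 × s
- matched: 0.5 × (1 − s)

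At s = 0.25 these are 0.125 and 0.375; at s = 0.5, 0.25 each; at s = 0.75, 0.375 and 0.125. The literal value is nearer below s = 0.5 and the matched value above it. The documents do not give s.

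**Raw arm means.** One affected subject moves an arm of 20 by 0.5/20 = 0.025 and an arm of 40 by 0.5/40 = 0.0125, which is 7% and 3.5% of 0.36. For frequency, Protocol 9.2.6 offers only that "only 2.3% subjects were discontinued or had missing data after randomisation in the 8 week GSKCH study 204763". That is a subject-level rate. If all of it were single-tooth loss in 2/3 subjects in one direction, the average shift would be 0.023 × 0.5 = 0.0115.

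**Primary ANCOVA.** When change is regressed on treatment and the same baseline, subtracting baseline lowers the baseline coefficient by 1 and leaves the treatment coefficient unchanged. Under the literal rule the analysis is therefore the same as an ANCOVA of the Week 8 score. The two readings differ only through the covariate of the affected subject, so for one such subject in an arm of 20 the shift is about 0.025 × slope. The slope is not in the documents. In 3,000 simulated 40/20/20 trials per slope (residual SD 0.8, tooth baselines 2 or 3 equally likely, one 2/3 negative-control subject losing the 3):

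| Assumed slope | Mean shift | Shift / 0.219 |
|---|---|---|
| 0.25 | 0.006 | 3% |
| 0.5 | 0.012 | 5% |
| 0.75 | 0.018 | 8% |
| 0.9 | 0.022 | 10% |

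**Several subjects affected.** A second simulation (40 v 20, 4,000 trials, Week 8 scores built as baseline plus a shift, so a slope near 1) gave a mean ANCOVA shift of about 0 when the lost tooth was random. When only the test arm lost teeth, and always the one with the higher baseline, the mean shift was −0.005 at a 2.3% loss rate and −0.024 at an assumed 10%.

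**The case for a change.** The strongest case for acting is that the sentence is incomplete in the one situation it addresses, that it concerns the primary endpoint, and that completing it costs little. Part of this stands. The text does not settle the baseline mean, the 0.5 gap is exact, and the choice should not be made with treatment codes in hand. The rank test has no baseline covariate to absorb the gap, although it would move only that subject's rank by a half-point step and the subject stays in Stratum 2 either way. Chance clustering is also possible: with random loss at 2.3%, the ANCOVA shift had a standard deviation of 0.015 across simulated trials, and the largest of 4,000 was 0.095. That is the equivalent of about four control subjects affected in the same direction (0.095/0.025 = 3.8) with a slope near 1.

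What does not stand is that the literal rule is an error. It can be the better estimate of the two-tooth change. Matching the covariate as well has its own price: a baseline covariate should be fixed before randomisation, and a matched one would depend on which tooth is evaluable afterwards and could differ between Week 4 and Week 8.

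The intent is also fairly clear. Every eligible test tooth has a qualifying baseline, so asking for validity at both times does little except pair the teeth. The mean-change wording for tactile threshold and VRS points the same way. Section 3.1 and the listing note are weak evidence against this, since one selects the assessment and the other describes a layout. The two tactile wordings give the same number whenever both teeth are present.

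**Conclusion.** No change to the plan is needed. SAP 4.4.1.1 leaves a detail open for a subject with exactly one evaluable tooth and unequal baseline scores. The two readings then differ by 0.5 for that subject, and in every other case they agree. The documents do not show which reading is nearer the two-tooth change, so calling the written rule wrong goes too far.

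The effect on the primary comparison is about 0.006 to 0.022 per affected subject in a 20-subject arm, or 3% to 10% of a standard error of 0.219, for assumed slopes of 0.25 to 0.9. The study is stated not to be powered for this comparison (Protocol 9.2.4), and a shift of this size would not alter how the magnitude is read.

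This rests on single-tooth loss being rare. That is plausible given the 2.3% subject-level figure, but no document gives a tooth-level rate. A programmer will meet the case, if at all, while building the analysis dataset, and can settle it there before unblinding.
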